2.3. *rTMS is a relatively new therapeutic modality that shows great promise in the treatment and evaluation of a variety of conditions and is already FDA-approved for the treatment of depression. However, various target stimulation parameters and protocols make comparison across research groups difficult, leading to a knowledge gap. Validating a systematic methodological approach in healthy people will allow comparison to previous work as well as establishing a baseline for moving forward to compare metaplasticity in brain disease states.*

3. Study Design

3.1. *This will be a randomized, sham-controlled, double blinded crossover trial in a healthy population.*

[figure not shown]

Figure 1: Subjects will enter the randomization at green diamond. Example shown for a subject following the red line through 3 interventions and another example shown in the blue line receiving a different order of interventions. They will be randomized to a three-visit crossover with a week separation between each visit. There will be four measures taken each visit (M1-M4), which will be approximately 10 minutes apart. Measures taken at each time point include: physiological measures (e.g. MEP), behavioral outcomes (e.g. reaction time) and exploratory outcomes. Study is completed at the end of visit 3 (red octagon). C tDCS=cathodal tDCS; A tDCS=anodal tDCS.

3.2. *Participants will be blinded to treatment group. A team investigator, off-line, will conduct the raw data analysis (e.g. MEP amplitude and CSP) and will be different than the investigator applying the noninvasive neurostimulation to the*

PROTOCOL TITLE: *Metaplasticity in the human motor cortex: validation of an experimental design and comparison of motor outcome measure sensitivity to change*

treatment group. This additional blinding of the data analysis will help to provide another protection against bias.

4. Inclusion and Exclusion Criteria

4.1. Individuals will be screened for eligibility by a study team member. The study team member will ask the potential participant a series of questions to determine whether or not they meet the inclusion/exclusion criteria.

4.2. Inclusion Criteria:

- a) Participant must be at least 18 years of age (all genders, races, and ethnicities)*
- b) Participant must have no current psychiatric or neurologic issues*
- c) Participant must not have any conditions listed in the exclusion criteria*
- d) Participant must be fluent in English*

Exclusion Criteria:

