- 6.1. *Study subjects will participate in three visits total. Each visit will consist of a visit length of 1 to 1 ½ hours in duration. The visits will be approximately one week apart. There will be no scheduled follow-up after the third subject visit. We anticipate that it will take 8 months to enroll all subjects. We expect to complete enrollment of all subjects and completion of experiments in 1 year. We expect data analysis and publication to occur within 2 years of study commencement.*

7. Study Endpoints

- 7.1. *The primary endpoint will be change in motor evoked potential (MEP) amplitude over the first dorsal interosseous (FDI) muscle of the dominant (right) hand pre- and post-intervention (tDCS and rTMS—time points M1-M3) as well as 10 minutes post intervention (time point M4). The secondary endpoint will be the comparison in an exploratory but systematic fashion various measures of motor cortex excitability (e.g. peak-to-peak amplitude change in motor evoked potential (MEP), the integrated area of the MEP (root mean square), the cortical silent period (CSP)), and behavioral measures (reaction time).*
- 7.2. *We will collect data on the safety of rTMS in this patient population including expected side effects: headache (expected 17% with transient headache that responds to simple analgesic) and nonspecific feelings of discomfort. We will collect data on rare but serious adverse events such as seizures (reported at 1.4%). No seizures have been reported in the literature on rTMS in the dystonia population thus far (Lefaucheur et al., 2014).*

8. Research Setting

- 8.1. *The study visits will all take place in the Noninvasive Neurostimulation Lab located on the 2nd floor of the Clinical and Translational Science Center (CTSC).*
- 8.2. *Potential subjects will be recruited and identified through the healthy participant registry through the CTSC as well as fliers placed throughout the Health Sciences Center and Main Campus.*

PROTOCOL TITLE: *Metaplasticity in the human motor cortex: validation of an experimental design and comparison of motor outcome measure sensitivity to change*

8.3. *Research procedures will be performed in the Noninvasive Neurostimulation Lab located on the 2nd floor of the CTSC. Analysis will be performed between the offices of [name], [name], and the CTSC Biostatistics core.*

8.4. *N/A*

8.5. *N/A*

9. Resources Available

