11.1. N/A

11.2. N/A

11.3. N/A

12. Study Procedures

12.1. *Visit 1: After informed consent, subjects will be seated in a comfortable chair. Surface EMG leads will be applied to clean and prepped skin over the right hand over the first dorsal interosseous muscle (FDI). The motor hotspot for FDI will be identified with TMS on the contralateral hemisphere. Resting motor threshold and active motor threshold will be determined.*

- **M1** (pre-tDCS measurement): neurophysiological outcome assessment (MEP, CSP) and behavioral outcome (reaction time task)
- **Priming Intervention** 10 min tDCS (cathodal, anodal or sham)
- **M2** (pre-tDCS measurement): neurophysiological outcome assessment (MEP, CSP) and behavioral outcome (reaction time task)
- **Inhibitory Intervention** 15 min rTMS over the dominant primary motor cortex at 1Hz
- **M3** (post-rTMS measurement): neurophysiological outcome assessment (MEP, CSP) and behavioral outcome (reaction time task)
- **M4** (10 minutes post-rTMS measurement): neurophysiological outcome assessment (MEP, CSP) and behavioral outcome (reaction time task)

PROTOCOL TITLE: *Metaplasticity in the human motor cortex: validation of an experimental design and comparison of motor outcome measure sensitivity to change*

Visit 2:

- **M1** (pre-tDCS measurement): neurophysiological outcome assessment (MEP, CSP) and behavioral outcome (reaction time task)
- **Priming Intervention** 10 min tDCS (cathodal, anodal or sham)
- **M2** (pre-tDCS measurement): neurophysiological outcome assessment (MEP, CSP) and behavioral outcome (reaction time task)
- **Inhibitory Intervention** 15 min rTMS over the dominant primary motor cortex at 1Hz
- **M3** (post-rTMS measurement): neurophysiological outcome assessment (MEP, CSP) and behavioral outcome (reaction time task)
- **M4** (10 minutes post-rTMS measurement): neurophysiological outcome assessment (MEP, CSP) and behavioral outcome (reaction time task)

Visit 3:

- **M1** (pre-tDCS measurement): neurophysiological outcome assessment (MEP, CSP) and behavioral outcome (reaction time task)
- **Priming Intervention** 10 min priming tDCS (cathodal, anodal or sham)
- **M2** (pre-tDCS measurement): neurophysiological outcome assessment (MEP, CSP) and behavioral outcome (reaction time task)
- **Inhibitory Intervention** 15 min rTMS over the dominant primary motor cortex at 1Hz
- **M3** (post-rTMS measurement): neurophysiological outcome assessment (MEP, CSP) and behavioral outcome (reaction time task)

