- **M4** (10 minutes post-rTMS measurement): neurophysiological outcome assessment (MEP, CSP) and behavioral outcome (reaction time task)

13. Data Analysis

13.1. Aim 1: To compare pre- and post- measures of cortical excitability after inhibitory and excitatory priming of the motor cortex. Hypothesis 1: We expect priming tDCS to affect the response to rTMS, namely we expect “inhibitory” cathodal tDCS to cause a reversal of the normal inhibitory effect of 1Hz rTMS. Hypothesis 2: We expect “excitatory” anodal tDCS to have no effect on the normal inhibitory effect of 1Hz rTMS. Hypothesis 3: We expect sham tDCS to have no effect on the normal inhibitory effect of 1Hz rTMS. We will use a MANOVA model (anodal, cathodal, and sham) and a specified number of

PROTOCOL TITLE: *Metaplasticity in the human motor cortex: validation of an experimental design and comparison of motor outcome measure sensitivity to change*

variables (time points—M1-M4). MANOVA assumes normality of the residuals and equality of variance across groups. In the case of violation of these assumptions, we will explore data transformations, including logarithmic, power, and inverse-normal transformations, to identify an analytic scale under which modeling assumptions are met. Should transformations not be adequate, we will employ non-parametric methods instead.

Exploratory Aim 2: To evaluate the sensitivity of motor outcome measures to changes in cortical plasticity. Hypothesis 1: We expect different measures of motor cortex excitability to be more sensitive than others at detecting changes in cortical excitability. We will be comparing in an exploratory but systematic fashion various measures of motor cortex excitability (e.g. peak-to-peak amplitude change in motor evoked potential (MEP) and the integrated area of the MEP (root mean square)) with the cortical silent period (CSP) and behavioral measures (reaction time). We will perform both a linear regression as well as a Principal Components Analysis (PCA) to identify which cortical excitability factors are most sensitive to change due to noninvasive neurostimulation.

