17.2. N/A

18. Risks to Subjects

18.1. TMS: *TMS is a safe procedure that has been used on many people to study the brain. Most people do not find the stimulation painful, but occasionally strong contractions of scalp muscles can cause some discomfort or headache. Headaches usually go away promptly with nonprescription medication. The noise of the TMS magnet may affect hearing, so participant will be fitted with earplugs. Magnetic stimulation will not be performed in people who have pacemakers, implanted pumps or stimulators, or who have metal objects inside the eye or skull. The risk of inducing a seizure with single, or paired-pulse, TMS is considered very low. Seizures from single/paired-pulse TMS have only been reported in subjects with medically-intractable epilepsy very rarely (0.0-3%). Safety studies using TMS in patients with neurological disorders have demonstrated no permanence.*

tDCS: *At the beginning of tDCS most people feel a tingling sensation that is present for a short period of time. Also, most people feel a warming sensation on the scalp that disappears after awhile. tDCS is known to be a safe procedure for several hundred patients at UNM, but in a few cases (1%) subjects have reported minor skin burns at the electrode spot. For example, a few subjects who had recently shaved their heads have reported transient redness and irritation at the stimulating electrode site. Prior to stimulation, your scalp will be checked for any redness or recent shaving of the head. If any of these are seen, we will pause or stop your participation in the study. You will be encouraged at the beginning of and throughout the tDCS procedure to report any pain or problems at the electrode sites that you may encounter throughout the procedure. Any problems, or evidence of redness or pain of the scalp, will result in the immediate stopping of stimulation. As with any contact between persons and electrical apparatuses, there is a slight possibility of electrical shock. To our knowledge, no studies have reported any electrical shock resulting from tDCS, and we do not expect this event to occur in our experiment. tDCS uses rubber electrode holders. If you think you may be sensitive or allergic to rubber or latex, please tell us before the start of the experiment. A few people in other studies have experienced drowsiness, excitement, or dizziness after tDCS.*

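### No safety contact is scheduled after the last session, so late or unresolved adverse events in one third of sessions are not actively sought

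*Combined protocol and SAP*

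**What the plan says.** Section 6.1 (Study Timelines) gives three visits per participant. On spacing: "The visits will be approximately one week apart". On length: "Each visit will consist of a visit length of 1 to 1 ½ hours in duration". It then rules out later contact: "There will be no scheduled follow-up after the third subject visit". The legend to Figure 1 in section 3.1 agrees: "Study is completed at the end of visit 3 (red octagon".

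Section 12.1 lists the same sequence at each visit: M1, 10 minutes of tDCS, M2, rTMS ("15 min rTMS over the dominant primary motor cortex at 1Hz"), M3 and M4. The M4 entry, the last item of the study, reads "10 minutes post-rTMS measurement): neurophysiological outcome assessment (MEP, CSP) and behavioral outcome (reaction time task". Neither this entry nor any other in 12.1 includes a question about adverse events.

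Sections 7.2 and 14.2 nevertheless promise safety data on rTMS: "headache (expected 17% with transient headache that responds to simple analgesic", discomfort, and seizure (1.4%). For tDCS, section 18.1 mentions minor skin burns in 1% and adds: "A few people in other studies have experienced drowsiness, excitement, or dizziness after tDCS". Section 14.3 has the safety data reviewed while the study enrols and runs, 14.5 plans no formal safety analysis, and 14.7 commits to regulatory reporting.

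**The concern.** Some of the harms that the protocol names unfold over time. A headache can start after the participant has left. Whether it is transient and responds to an analgesic can be seen only some time after it begins. Drowsiness or dizziness after tDCS may also be noticed later. After sessions 1 and 2 the participant returns and can be asked, or can volunteer the event. After session 3 nobody is scheduled to ask, and no visible rule says how an event still open at the end of that visit is tracked.

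The stake is the completeness of the safety record. The principal investigators are the medical monitors (14.1), and their ongoing review works only on events that reach them. Enrolment is expected to take 8 months, so a late event in an early finisher could inform the review while others are still being stimulated. The method is also meant to be carried into patient populations (1.1), so a gap in the healthy-volunteer harm data would go with it.

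**Working it through.** The plan states no adverse-event window, so there is no figure of its own to reproduce. The check compares, session by session, the time from the end of rTMS to the last scheduled contact.

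**Inputs.** Gap between visits about 7 days (6.1); visit length 60 to 90 minutes (6.1); tDCS 10 minutes, rTMS 15 minutes, M4 at 10 minutes after rTMS (12.1); 16 participants, ceiling 20 (5.2, 5.3); headache 17% and seizure 1.4% (7.2, 14.2).

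**Sessions 1 and 2.** The next scheduled contact is the next visit: 7 × 1,440 = 10,080 minutes. This is an opportunity inferred from the visit spacing, not a specified collection window.

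**Session 3, after rTMS.**
- Lower bound: 10 minutes, at M4.
- Upper bound, allowing no time for set-up, M1 or M2: 60 − 10 − 15 = 35 minutes for a 60-minute visit, and 90 − 10 − 15 = 65 minutes for a 90-minute visit.
- Ratio to sessions 1 and 2: 10,080 / 65 = 155 up to 10,080 / 10 = 1,008. If the gap between visits ranged from 5 to 9 days (assumption), the ratio would run from 5 × 1,440 / 65 = 111 to 9 × 1,440 / 10 = 1,296.

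**Session 3, after tDCS.** M4 comes at least 15 + 10 = 25 minutes after tDCS, plus the time taken by M2. The 10-minute figure therefore does not apply to the tDCS harms.

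**Share of sessions affected.** 16 / (3 × 16) = 16/48 = 33%; at the ceiling, 20/60 = 33%.

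**Events arising from final sessions, at any time.** The protocol does not say whether its rates are per session or per participant, so both are shown as assumptions for 16 participants (20 in brackets).
- Per session: headaches 16 × 0.17 = 2.7 (3.4); seizures 16 × 0.014 = 0.22 (0.28).
- Per participant, spread evenly over three sessions: headaches 2.72 / 3 = 0.9 (1.1); seizures 0.224 / 3 = 0.07 (0.09).

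Only the part of these that begins after the participant leaves would be missed. Call that share d. If events are spread evenly over sessions and every earlier one is recalled at the next visit, the pooled under-count is d/3. The documents say nothing about d, so all that follows is a range from 0 (d = 0) to one third (d = 1).

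**The case against.** The strongest reply has four parts.

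1. **The week is not a window.** A reader might infer that the plan collects events for 7 days after sessions 1 and 2 and for 10 minutes after session 3. It does not say so: visits 2 and 3 list no adverse-event question either. This stands. What differs between sessions is the chance to learn of an event, and the broader gap is that no method or window is defined for any session.

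2. **No comparison is biased.** A reader might infer that the condition given last is at a disadvantage, so that counts by condition cannot be compared. The documents do not support this. Order is randomised, rTMS is given in every session, and 14.5 plans no formal safety analysis. Sixteen does not divide by three, but a 6/5/5 split with 17% per session and d = 0.50 (assumption) shifts the expected difference by only 1 × 0.17 × 0.50 = 0.085 headaches. A larger imbalance is possible because the allocation method is not described, but that is a separate matter.

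3. **Withdrawals are not without contact.** Under 15.5 a participant who withdraws must speak with the principal investigator or the coordinator. For someone withdrawing between visits, that is a contact after the last session. This stands, although no safety question is attached to it.

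4. **Some handling exists.** Section 6.1 excludes scheduled follow-up, not reports that a participant makes unprompted. The principal investigator is on site at each visit (16.7), events are reported under the regulations (14.7), and treatment is available at the participant's expense (22.4, 24.2). The consent form is a separate attachment (26.1) and may tell participants to report later symptoms. All of this is fair, but none of it is a scheduled contact. It leaves ascertainment after the final session to the participant's initiative.

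**Conclusion.** The point holds as a gap in safety ascertainment. Followed as written, the protocol does not actively seek late-onset or unresolved events after the final session, which is one third of all sessions (16 of 48, or 20 of 60), although it undertakes to collect such data. Scheduled observation there ends between 10 minutes and, at most, 35 to 65 minutes after rTMS.

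Under-ascertainment of late events in those sessions is probable. It rests on two premises: some events begin or persist after the participant leaves, and not all are volunteered. The documents give no figure for either, so a percentage under-count would be an assumption and not a finding. The MEP analysis and the exploratory comparison of outcome measures are untouched. This is a worthwhile, inexpensive improvement, not a threat to the trial's main result.

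**What to change.** - In 6.1, replace the sentence that rules out follow-up with one brief phone or e-mail safety contact after each participant's last session. The investigators should set the interval, comparable to the gap between visits so that every session has a similar opportunity for events to be reported.
- In 12.1, add the same short adverse-event question at the start of visits 2 and 3. Ask it also in the withdrawal conversation under 15.5, where the participant agrees.
- In section 14, state how events still open at the last contact are tracked in the safety record.

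The cost is 16 to 20 short contacts by existing staff, one line in the consent form, and holding contact details slightly longer. No new personnel or procedures are needed.

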ICH-GCP E6 can be accessed by copying and pasting this URL into your browser: <http://www.fda.gov/downloads/Drugs/Guidances/ucm073122.pdf>

Table of Contents

1. Objectives	4
2. Background	4
3. Study Design	5
4. Inclusion and Exclusion Criteria	5
5. Number of Subjects	6
6. Study Timelines	6
7. Study Endpoints	6
8. Research Setting	7
9. Resources Available	7
10. Prior Approvals	7
11. Multi-Site Research	8
12. Study Procedures	8
13. Data Analysis	8
14. Provisions to Monitor the Data to Ensure the Safety of Subjects	9
15. Withdrawal of Subjects	9
16. Data Management/Confidentiality	9
17. Data and Specimen Banking	11
18. Risks to Subjects	11
19. Potential Benefits to Subjects	11
20. Recruitment Methods	12
21. Provisions to Protect the Privacy Interests of Subjects	12
22. Economic Burden to Subjects	12
23. Compensation	13
24. Compensation for Research-Related Injury	13
25. Consent Process	14
26. Documentation of Consent	16
27. Study Test Results/Incidental Findings	17
28. Sharing Study Progress or Results with Subjects	18
29. Inclusion of Vulnerable Populations	18
30. Community-Based Participatory Research	19
31. Research Involving American Indian/Native Populations	19
32. Transnational Research	19
33. Drugs or Devices	19
Checklist Section	20

1. Objectives

1.1. *The overall objective is to validate the methodology of a metaplasticity experimental design by assessing change in motor excitability after administration of priming transcranial direct current stimulation (tDCS) followed by repetitive transcranial magnetic stimulation (rTMS) in healthy human participants. Our primary objective is to compare pre- and post-measures of cortical excitability before priming tDCS (anodal, cathodal or sham) [M1], directly after priming tDCS [M2], directly after inhibitory rTMS [M3], and 10 minutes after inhibitory rTMS [M4]. Our secondary objective is to evaluate the sensitivity of motor excitability outcome measures response to the noninvasive neurostimulation (e.g. rTMS and tDCS). Our future direction is to apply this validated protocol in patient populations to better understand how disease states affect metaplasticity.*

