13.2. *Power analysis:* Sixteen subjects will be enrolled for this study according to the MANOVA model (anodal, cathodal, and sham) and a specified number of variables (time points—M1-M4) at the significance level of $\alpha=0.05$ and 80% power to correspond to the very large effect size. We have based the calculation on the very large effect size as seen in Quartarone et al., 2005. The desired sample size was found to be 16 patients per treatment arm. We will fulfill this sample size requirement through a crossover trial as all 16 subjects will participate in each treatment arm. We would request a recruitment ceiling of 20 subjects to account for subject dropout and if a subject were to meet exclusion criteria after signing the consent.

14. Provisions to Monitor the Data to Ensure the Safety of Subjects

14.1. The PIs will consist of the medical monitoring team for this study due to its minimal risk status.

14.2. We will collect data on the safety of rTMS including expected side effects: headache (expected 17% with transient headache that responds to simple analgesic) and nonspecific feelings of discomfort. We will collect data on rare but serious adverse events such as seizures (reported at 1.4%).

14.3. The safety data will be reviewed on an ongoing basis during enrollment and conduct of the study.

14.4. We plan to follow the most recent safety recommendations from expert consensus panels on rTMS.

14.5. We have no planned formal analysis of the safety data.

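### The pre-tDCS baseline M1 is used only as a change-score origin or as a MANOVA response; making it a covariate would recover some power at no cost in data

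*Combined protocol and SAP*

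**What the plan says.** Section 7.1: "The primary endpoint will be change in motor evoked potential (MEP) amplitude over the first dorsal interosseous (FDI) muscle", across M1 to M3 and again at M4. Which difference is primary (M3−M1, M3−M2 or M4−M1) is not fixed.

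Section 1.1 counts M1 among the measures to be compared: "compare pre- and post-measures of cortical excitability before priming tDCS (anodal, cathodal or sham) [M1", followed by M2 to M4.

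Section 13.1 sets out the primary model: "We will use a MANOVA model (anodal, cathodal, and sham) and a specified number of" outcomes, which it then gives as M1 to M4. Sections 5.3 and 13.2 size the trial "according to the MANOVA model (anodal, cathodal, and sham) and a specified number of variables (time points—M1-M4". Both set α at 0.05 and power at 80%.

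Section 12.1 places M1 before tDCS at each of the three visits. It gives M2 the same pre-tDCS label, but M2 comes after tDCS in the listed order, and 1.1 places it directly after priming. M1 is therefore the only true session baseline.

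No section names M1 as a covariate or constrains its mean to be equal across conditions. Section 13.1 names no participant, period or sequence term, and does not say whether the condition test or the condition-by-time test is meant. Its only contingencies are transformations and non-parametric methods.

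**The concern.** A measurement taken before the randomised intervention carries no information about that intervention's effect, but it does help predict the later measurements. The plan uses it less well than it could on either reading.

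- As a MANOVA response, M1 takes test degrees of freedom for a variable on which no effect of that visit's condition is possible. A difference between conditions at M1 also feeds the overall condition test.
- As a subtracted baseline, M1 is removed with a slope of one, whatever its real correlation with the later value. When that correlation is modest, this adds noise.

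With 16 people, a ceiling of 20 and a sample size resting on an unquantified effect, precision matters. The baseline is already being collected.

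**Working it through.** **The plan's own figure.** Sixteen per arm can be neither confirmed nor refuted, because 13.2 says only "We have based the calculation on the very large effect size as seen in" a cited study and gives no number. Solving backwards, 16 per arm with 80% power corresponds to f²(V) ≈ 0.171 in a three-group, four-variable Pillai MANOVA. It also corresponds to a standardised difference of about 1.0 between two arms.

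**Inputs.** From the documents: 16 people, three conditions, four time points, α = 0.05, 80% power. Assumed: ρ, the within-person, session-to-session correlation of M1 with the later measure, taken as 0.3 to 0.7 (0.9 also shown), with equal variances. Stable differences between people drop out once participant is in the model.

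**Case A: the MANOVA as stated (3 × 16, Wilks).** Error df = 48 − 3 = 45.

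- Four responses: F df are 2×4 = 8 and 2(45 − 4 + 1) = 84. Power of 80% needs noncentrality 16.44.
- Three responses with M1 as covariate: error df is 44, and F df are 2×3 = 6 and 2(44 − 3 + 1) = 84. With no condition effect on M1 the noncentrality is unchanged, and power is 85%.

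**Case B: change from M1.** In units of the within-person variance, the contrast variance is proportional to 2(1 − ρ) for the change score and 1 − ρ² after adjustment, a ratio of (1 + ρ)/2. With participant, condition and period fitted, error df fall from 28 to 27 when the slope is estimated, which multiplies the ratio by 1 + 1/26. The 80% reference is a t noncentrality of 2.902 on 28 df; adjusted power divides this by the square root of the net ratio.

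| ρ | 2(1 − ρ) | 1 − ρ² | Ratio | Net ratio | Power, from 80% | 16 / net ratio |
|---|---|---|---|---|---|---|
| 0.3 | 1.40 | 0.91 | 0.65 | 0.675 | 93% | 23.7 |
| 0.5 | 1.00 | 0.75 | 0.75 | 0.779 | 89% | 20.5 |
| 0.7 | 0.60 | 0.51 | 0.85 | 0.883 | 85% | 18.1 |
| 0.9 | 0.20 | 0.19 | 0.95 | 0.987 | 80% | 16.2 |

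The last column is the number of change-score participants that 16 adjusted participants are worth. The net ratio reaches 1 at ρ = 25/27 ≈ 0.93. Below ρ = 0.5 the change score is noisier than ignoring M1 (1.40 against 1.00 at ρ = 0.3).

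**Simulation** (16 people × 3 conditions, participant in the model, equal correlations, Pillai, 4,000 runs). Entries are rejection rates at ρ = 0.3 / 0.5 / 0.7.

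| Scenario (one condition shifted) | M1–M4 condition test | Change from M1 | M2–M4 adjusted for M1 |
|---|---|---|---|
| No difference anywhere | 4 / 4 / 4% | 5 / 4 / 4% | 5 / 4 / 4% |
| 0.8 SD at M3 and M4 | 58 / 68 / 87% | 51 / 66 / 90% | 65 / 74 / 91% |
| 1 SD at M1 only | 56 / 70 / 91% | 59 / 75 / 95% | 10 / 24 / 61% |

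For a 1 SD shift of the whole session (M1 to M4), a separate simulation gives about 86 / 74 / 64% for the M1–M4 condition test, 5% for the change score and 47 / 26 / 14% after adjustment. The Pillai runs give 83 / 71 / 60%, about 5% and 45 / 24 / 14%.

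For scale, the chance M1 difference between two conditions has SD √(2/16) = 0.35 within-person SD. A 1 SD shift therefore represents carry-over rather than ordinary chance.

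**The case against.** **The planned MANOVA already uses M1.** This stands. When the condition does not affect M1, the joint test exploits its correlation with M2 to M4 and loses only degrees of freedom. The gain over that test is about 5 points in Case A and 4 to 7 points in the simulation. The larger figures in Case B apply only to a change-score analysis.

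**The gain depends on the contrast.** This stands. The hypotheses concern the response to rTMS, for which M3 minus M2 is a natural measure. M1 is not subtracted there, and with equal correlations Cov(M3 − M2, M1) = ρ − ρ = 0. In simulation, adding M1 moved power from 65/82/96% to 64/80/96%. Under a condition-by-time test, four time points reduce to three contrasts, so M1 takes no extra response degrees of freedom and acts as in a change score (Case B). A reader might infer that the loss holds whichever contrast is chosen, but 7.1 and 13.1 leave the contrast open and it does not.

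**Type I error is sound.** This stands. A reader might infer that baseline differences make the planned test invalid. Randomised order makes M1 equal in expectation without carry-over, and simulated null rejection was 4 to 5%.

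**Adjustment can do worse under carry-over.** This also stands. If a whole session shifts, the change score rejects at about 5% and the adjusted analysis more often, though still less often than the M1–M4 condition test.

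**Change from baseline is a legitimate quantity.** True, and Hypothesis 1 predicts a reversal of sign that adjusted between-condition contrasts alone would not show. That is a reason to report both; it does not justify leaving M1 as a tested response.

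**Conclusion.** The point holds as a matter of efficiency. M1 is a baseline that the plan treats as a response or a subtraction and never as a covariate. Covariate use lifts power from 80% to about 85% relative to the stated MANOVA. Relative to a change from M1, the contrast variance falls by about 32%, 22% or 12%, giving 93%, 89% or 85% power at ρ of 0.3, 0.5 or 0.7, with next to nothing gained at 0.9 or above.

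These figures rest on an assumed ρ, equal variances and no carry-over. They do not apply to M3 minus M2. The documents do not support reading this as an inflated false-positive rate or as a complete loss of the baseline's information. Nor would adjustment remove a real M1 difference; it only reduces its influence. The change is worth making because it is nearly free and the trial is small.

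**What to change.** In 7.1 and 13.1:

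- Analyse (log) MEP at the post-baseline time points, with the same session's (log) M1 as covariate and with participant, period and condition in the model. If participant is a random effect, add the participant's mean M1 so that the slope is a within-person one.
- Remove M1 from the tested responses, and align the description in 5.3 and 13.2.
- State which contrast and time point are primary, since the gain depends on this.
- Report the adjusted cathodal–sham and anodal–sham contrasts, and each condition's change from baseline so that the reversal in Hypothesis 1 can be seen.
- Tabulate M1 by condition and visit as the carry-over check, and show the change-score analysis as a sensitivity analysis, because adjustment is the weaker of the two if a whole session shifts.
- Correct the M2 label in 12.1 so that the covariate is unambiguous.

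The cost is analysis wording and one model degree of freedom, with no extra visit, measurement or participant. It should be settled before outcome data are seen, because choosing how to handle the baseline afterwards can itself introduce bias.
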